9.1.2 Characterization of immune infiltration within prostate tissue

The effect of ibrutinib on the number of infiltrating B cells and T cells will be assessed by immunohistochemistry with antibodies to CD20, IL-10, CD3, CD8, CD4, and FoxP3. Prostate tumor tissue from diagnostic core biopsy specimens and post-treatment prostatectomy tissue specimens will be analyzed. Infiltrate will be scored by the number of cells/ μm^2 ; thus, the number of inflammatory cells will be normalized to the unit area. For each patient, the change in the number of immune cell infiltration from the pre-treatment biopsy to post-treatment prostatectomy tissue specimens will be represented by the ratio of post-treatment

prostatectomy versus pre-treatment biopsy tissue specimen. IHC for immune infiltration will be performed in the [name] Lab at Washington University.

9.1.3 Characterization of Circulating and Intratumoral T and B cells via TCR and BCR sequencing

Next-generating sequencing (NGS) of the VDJ region of T-cell receptors (TCRs) and B-cell receptors (BCRs) will be utilized to define the TCR and BCR repertoire in the blood and tumor tissue before and after ibrutinib therapy. This approach allows the tracking of T and B cell clones in the blood and tissue over time to assess their expansion and migration. TCR and BCR sequencing will be carried out by Sequenta, Inc.

9.1.4 PD-L1 Expression in Tumor and Tumor-Infiltrating Lymphocytes

The expression level of PD-L1 on tumor and tumor-infiltrating lymphocytes (TILs) will be examined using immunohistochemistry on diagnostic core biopsy specimens and post-treatment prostatectomy tissue specimens. The expression level of PD-L1 will be graded by an expert pathologist to determine the impact of neoadjuvant ibrutinib on PD-L1 expression in prostate cancer cells and TILs. IHC for PD-L1 will be performed in the [name] Lab at Washington University.

9.1.5 Btk expression

The expression level of Btk on prostate cancer tissue from core biopsy before surgery will be examined using immunohistochemistry with anti-Btk antibody (Santa Cruz Inc., Santa Cruz, CA, USA; sc-1107). IHC for total Btk and phospho-Btk will be performed in or the [name] Lab at Washington University.

9.1.6 PSA

The utility of a decline in PSA as a marker of response to neoadjuvant therapies is not well defined. However, the proportion of patients with PSA response, defined as $\geq 50\%$ PSA decline, will be reported.

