1.5 Correlative Studies

This study aims to evaluate the immunomodulatory and cytotoxic effects of ibrutinib in prostate cancer patients by comparing their pre-treatment prostate biopsy tissue to post-treatment prostatectomy tissue. Specifically, immunohistochemistry and genomic analysis will be carried out to analyze the following:

1. Characterize the tumor and immune cell subsets
2. Explore the location of tumor infiltration lymphocytes (e.g., tumor center, tumor and benign tissue interface)
3. Characterize BCR and TCR clonality and diversity
4. Examine PD-L1 expression in tumor and immune-infiltrating immune cells
5. Examine Btk expression in B cells and tumor cells
6. Assess rate of downstaging and pT0 rate
7. Assess rate of PSA decline

In addition, serum and blood will be analyzed to characterize circulating immune cell subsets in response to treatment.

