2.2.2 Secondary Endpoints

The changes in the frequency and number of circulating CD19+ B cells, CD25^{high}CD27^{high}CD86^{high} B regulatory cells, and CD3+, CD8+, CD4+FOXP3- and CD4+FOXP3+ T cells induced by neoadjuvant ibrutinib in patients with localized prostate cancer by flow cytometry. Patients will be considered to have a positive response if there is ≥ 2 fold decrease from pre-treatment to post-treatment, or considered to have a negative response if there is < 2 fold decrease. The proportion of patients who have “positive” responses will be evaluated.

The proportion of patients who achieve $\geq 50\%$ PSA decline, pathologic down-staging and/or pathologic T0 at RP after neoadjuvant ibrutinib in men with localized prostate cancer.

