3 STUDY DESIGN

3.1 Characteristics

This is a single center phase 2 open label study starting with a safety lead-in ibrutinib administered as neoadjuvant therapy in patients with localized prostate cancer. We believe that the dose of ibrutinib 840mg x 4 weeks will be well tolerated in patients with localized prostate cancer based on current trial data on ibrutinib but to ensure safety, we will start with a safety run-in. Previously at UCSF, 3 patients were enrolled to the 840 mg/d x 2 weeks dose level. No DLTs were observed. Beginning at WUSM, patients will be enrolled at the dose level of 840 mg/d x 4 weeks. If there are fewer than 2 DLTs, the Phase II dose expansion study will open and enroll up to an additional 18 patients to be treated with ibrutinib 840mg PO daily for 4 weeks.

If there are ≥ 2 DLTs in the safety lead-in, dosing will be de-escalated as follows:

- Level -1: 840 mg/d x 2 weeks, followed by de-escalation if ≥ 2 DLTs to Level -2
- Level -2: 560 mg/d x 2 weeks

In each enrolled patient, neoadjuvant ibrutinib therapy will be followed by radical prostatectomy (RP) performed 7 to 12 days after the last dose of ibrutinib. Pre-treatment and RP tissue will be evaluated for immunologic characterization, Btk expression and pathologic response. The proportion of patients achieving $\geq 50\%$ PSA decline will be assessed. Serum will also be obtained to characterize circulating immune response. All patients will be followed clinically for 4 weeks after RP to monitor for adverse events.

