12.6.3 Analysis of Secondary Endpoints

12.6.3.1 Circulating immune subsets

For each patient, flow cytometry of circulating immune cell subsets will also be performed on pre-treatment blood and again after RP. Established flow

cytometry panels will examine B cell and T cell populations. Immune cell quantification will be summarized by changes from baseline to after treatment using descriptive statistics. Furthermore, paired Wilcox on signed-rank test will be applied to test the pre-post treatment changes. When available, immune cells digested from resected tumor tissues will also be assessed by flow cytometry.

12.6.3.2 Cytotoxic effects and clinical benefits: rate of downstaging, pT0 rate, $\geq 50\%$ PSA decline (phase II)

Point estimates and 95% confidence intervals of pathologic T0 rate at the time of RP will be obtained for phase 2 subjects treated with ibrutinib. Pathologic T0 rate at the time of RP will be compared with the null hypothesis rate separately by using binomial test.

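### PSA is planned only as the share of men with a ≥50% fall, so a consistent moderate fall in the paired values already collected could look the same as no change

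*Combined protocol and SAP*

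**What the plan says.** Section 2.2.2 lists the secondary endpoint as "The proportion of patients who achieve $\geq 50\%$ PSA decline, pathologic down-staging and/or pathologic T0 at RP". Section 3.1 repeats the binary form: "The proportion of patients achieving $\geq 50\%$ PSA decline will be assessed". Section 9.1.6 opens with a caution, "The utility of a decline in PSA as a marker of response to neoadjuvant therapies is not well defined", and continues "However, the proportion of patients with PSA response, defined as $\geq 50\%$ PSA decline, will be reported". The only other wording is an item in the correlative list of section 1.5, "Assess rate of PSA decline", which is neither defined nor tied to an analysis.

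In the statistical section, the heading of 12.6.3.2 reads "Cytotoxic effects and clinical benefits: rate of downstaging, pT0 rate, $\geq 50\%$ PSA decline (phase II"), but the text beneath it concerns pT0 only: "Point estimates and 95% confidence intervals of pathologic T0 rate at the time of RP will be obtained for phase 2 subjects treated with ibrutinib", followed by a binomial test of the pT0 rate. No interval is specified even for the PSA share.

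The preceding subsection, 12.6.3.1, treats circulating immune subsets differently. They get descriptive statistics of change from baseline and a paired Wilcoxon signed-rank test that "will be applied to test the pre-post treatment changes".

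PSA is drawn at screening, Day 1, Day 29 and the post-RP visit (sections 8.1 and 8.2; data schedule in section 11). RP falls on Day 36 to 41.

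**The concern.** PSA is continuous and each man has pre-treatment and end-of-treatment values, so he is his own control. Reducing the pair to whether the fall reached 50% discards the size of the change. The other two measures of the objective, down-staging and pT0, are also yes/no, so the objective has no graded measure.

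At stake is what the PSA line of the report can show. If PSA fell moderately in nearly every man, the planned output could be zero or close to it, and a reader could not tell that from a PSA that did not move. Equally, a truly flat PSA could not be shown to be flat.

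There is a related gap. The endpoint does not name the two samples that define the decline. There are two pre-treatment draws, and the last draw follows removal of the prostate, so it cannot reflect a drug effect.

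**Working it through.** **Plan's own figure.** There is none to reproduce: the documents give no null rate, target, test, power or variance for PSA.

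**Inputs.** N = 24 (section 3.2), all assumed to have paired PSA. The cut is a post/pre ratio of 0.5 or less (9.1.6). A median fall d of 15–30% and an SD s of log(post/pre) of 0.2–0.5 are assumptions.

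**Step 1: strictly uniform fall.** Any common fall below 50% gives 0/24 responders. The exact two-sided 95% upper limit is 1 − 0.025^(1/24) = 0.142, so the interval is 0–14.2%. With no change in any man the output is again 0/24 with the same interval.

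**Step 2: allow spread.** Take log(post/pre) as normal with mean ln(1 − d) and SD s. Then

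P(fall ≥50%) = Φ{[ln 0.5 − ln(1 − d)] / s}.

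Example, d = 0.20 and s = 0.3: (−0.693 + 0.223)/0.3 = −1.567, so P = 0.0586. Expected responders are 24 × 0.0586 = 1.41, and the chance of none is (1 − 0.0586)^24 = 0.235.

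Expected responders out of 24:

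| Median fall | s = 0.2 | s = 0.3 | s = 0.4 | s = 0.5 |
|---|---|---|---|---|
| 15% | 0.1 | 0.9 | 2.2 | 3.5 |
| 20% | 0.2 | 1.4 | 2.9 | 4.2 |
| 30% | 1.1 | 3.1 | 4.8 | 6.0 |

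**Step 3: size of the loss, as illustration only.** The plan has no PSA test, so a yardstick must be borrowed. Section 12.3 uses 5% against 20% and a threshold of 4 responders for a 2-fold decrease in B cells. With N = 24, four or more responders has exact one-sided α = P(X ≥ 4 | 0.05) = 0.030 and power P(X ≥ 4 | 0.20) = 0.736. (Section 12.3 states 0.044 and 0.818; that mismatch concerns the B-cell endpoint and plays no part here.) Applying the same rule to PSA, and comparing it with a one-sided signed-rank test at the same α (20,000 simulated trials per cell, exact null distribution), for a 20% median fall:

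| s | Responder rule | Signed-rank test |
|---|---|---|
| 0.2 | 0.00 | 1.00 |
| 0.3 | 0.05 | 0.93 |
| 0.4 | 0.32 | 0.75 |
| 0.5 | 0.62 | 0.56 |

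At s = 0.5 the advantage has gone. But with no effect at all, P(fall ≥50%) = Φ(−0.693/0.5) = 0.083, already above the borrowed 5% null, so the responder rule no longer holds its level there.

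**The case against.** The strongest reply is that nothing hangs on the PSA share. It is one reported line with no null rate, test or decision attached. The synopsis ties this objective to pT0 alone, and PSA is handled like the other yes/no measures of its objective. The rule and rates in Step 3 belong to a tissue endpoint, so there is no planned PSA power to lose. The documents give no expected PSA effect for ibrutinib. If spread is wide, several men would cross 50%: a 30% median fall with s = 0.4 gives about 5 of 24 responders, with roughly a 0.5% chance of none. The raw values are collected, so the size of change could be summarised later. All of this stands, and it limits the point to a modest one. It does not supply the missing summary, and a summary chosen after the data are seen is weaker than one written down beforehand.

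A second reply is that the trial is single-arm and the 12 reference patients supply RP tissue only (section 12.7), so a paired test would flag any consistent drift, drug-related or not. That also stands and governs the labelling. The same limit applies to the ≥50% share and to the paired test already planned in 12.6.3.1.

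Two stronger readings are tempting and are not supported. A reader might infer that the protocol itself calls the 50% cut poorly defined. Section 9.1.6 says that of PSA decline as a response marker, a caution that applies equally to a continuous analysis. A reader might also infer that the trial would report little or no cytotoxic effect. Only the PSA line would read that way, because down-staging and pT0 are reported separately.

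**Conclusion.** The point holds as a gap in the analysis of one component of a secondary objective. The plan gives PSA only a ≥50% share, with no interval, and says nothing about the size of change although paired pre-surgery values will exist. The firm result is that a strictly uniform 15–30% fall and a flat PSA both give 0/24 (0–14.2%). Beyond that, the loss depends on the unknown spread, under a normal model for log change: large at s of 0.2–0.3, smaller at 0.4 and gone by about 0.5. The power figures are illustrative and are not properties of the plan. The fix is worth making because it costs almost nothing, but it does not affect the primary endpoints or the sample size.

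**What to change.** In sections 9.1.6 and 12.6.3.2:

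- Name the PSA baseline (screening or Day 1, or a stated rule combining them) and the Day 29 pre-RP sample as the post-treatment value. State that the post-RP sample is not used for this endpoint.
- Keep the proportion with a ≥50% fall and give it an exact 95% CI.
- Add the within-patient post/pre PSA ratio, as a median or geometric mean with 95% CI, a paired signed-rank test on log PSA in line with 12.6.3.1, and a per-patient waterfall plot.
- Label the paired analysis descriptive, not controlled for multiplicity, and not attributable to the drug, because there is no untreated PSA control.
- Define the PSA item in section 1.5 in the same terms, or remove it.

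The cost is a few sentences of plan text and one more secondary analysis. No extra samples, visits or patients are needed.

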9.1.7 Pathologic Response

The proportion of patients with down-staging of disease by Gleason score will be reported. The proportion of patients with pathologic complete response (pT0) at the time of prostatectomy will be reported.

9.2 Evaluation of Safety

The following will be collected to evaluate safety:

- Adverse events (including SAEs and deaths)
- Physical examinations
- Vital signs
- ECOG performance status
- Laboratory test results

Analyses will be performed for all patients having received at least one dose of study drug. The study will use the CTCAE v4.03 for reporting of non-hematologic adverse events and modified criteria for hematologic adverse events.

10 DATA AND SAFETY MONITORING

In compliance with the Washington University Institutional Data and Safety Monitoring Plan, the Principal Investigator will provide a Data and Safety Monitoring (DSM) report to the Washington University Quality Assurance and Safety Monitoring Committee (QASMC) semi-annually beginning six months after accrual has opened (if at least one patient has been enrolled) or one year after accrual has opened (if no patients have been enrolled at the six-month mark).

For phase I dose escalation studies, Principal Investigator will review all patient data at least monthly (or before each dose-escalation if occurring sooner than monthly), and provide a semi-annual report to the Quality Assurance and Safety Monitoring Committee (QASMC). For phase II or dose expansion cohorts of a phase I study, the Principal Investigator will review all patient data at least every six months, and provide a semi-annual report to the QASMC. This report will include:

- HRPO protocol number, protocol title, Principal Investigator name, data coordinator name, regulatory coordinator name, and statistician
- Date of initial HRPO approval, date of most recent consent HRPO approval/revision, date of HRPO expiration, date of most recent QA audit, study status, and phase of study
- History of study including summary of substantive amendments; summary of accrual suspensions including start/stop dates and reason; and summary of protocol exceptions, error, or breach of confidentiality including start/stop dates and reason
- Study-wide target accrual and study-wide actual accrual
- Protocol activation date
- Average rate of accrual observed in year 1, year 2, and subsequent years
- Expected accrual end date and accrual by cohort
- Objectives of protocol with supporting data and list the number of participants who have met each objective
- Measures of efficacy (phase I studies only if efficacy is objective of the protocol)
- Early stopping rules with supporting data and list the number of participants who have met the early stopping rules
- Power analysis and/or interim analysis (if described in the protocol)
- Summary of toxicities separated by cohorts with the number of dose-limiting toxicities indicated
- Abstract submissions/publications
- Summary of any recent literature that may affect the safety or ethics of the study

The study principal investigator and Research Patient Coordinator will monitor for serious toxicities on an ongoing basis. Once the principal investigator or Research Patient Coordinator becomes aware of an adverse event, the AE will be reported to the HRPO and QASMC according to institutional guidelines.

11 DATA SUBMISSION SCHEDULE

Case report forms with appropriate source documentation will be completed according to the schedule listed in this section.

Case Report Form	Submission Schedule
Original Consent Form	Prior to registration
On-Study Form Medical and Surgical History	Prior to starting treatment
Concomitant Medications Form Toxicity Form	Continuous
PSA Form	Baseline, Week 1, Week 5, Post-RP Follow-Up Visit
Research Blood Form	Baseline, Week 5, Post-RP Follow-Up Visit
Treatment Summary Form	Completion of treatment
RP Form	Time of surgery
Progression Form	Time of disease progression
MedWatch Form	See Section 7.0 for reporting requirements
Death Form	At time of death

11.1 Adverse Event Collection in the Case Report Forms

All adverse events that occur beginning with start of treatment (minus exceptions defined in Section 7.0) must be captured in the Toxicity Form. Baseline AEs should be captured on the Medical History Form.

Participant death due to disease progression should be reported on the Toxicity Form as grade 5 disease progression. If death is due to an AE (e.g. cardiac disorders: cardiac arrest), report as a grade 5 event under that AE. Participant death must also be recorded on the Death Form.

12 STATISTICAL CONSIDERATIONS AND EVALUATION OF RESULTS

12.1 Study Endpoints

See Section 2.4 for study endpoints.

12.2 Study Design

This is a single center phase 2 open label study of neoadjuvant ibrutinib in patients with localized prostate cancer.

12.3 Sample Size and Power Estimate

For this phase 2 study, the primary endpoint is the change of B cells between the pre-treatment biopsy and post-treatment RP specimen. Each patient's response to neoadjuvant ibrutinib will be a binary classification. Patients will be considered to have a

“positive” response if there is >2 fold decrease in the number of B cells, or considered to have a “negative” response if there is <2 fold decrease in the number of B cells. The accrual of 18 patients to the phase 2 trial and incorporation of 6 patients who received ibrutinib at MTD in the safety lead-in (a total of 24 evaluable subjects) will be sufficient to determine whether 20% or more of the cohort achieves this 2 fold decrease in B cells, compared to a null response of 5% or less of a reference group of patients who underwent RP without neoadjuvant treatment. This comparison has a power of 0.818 at a significance level of 0.044 based on a one-sided binomial exact test. If 4 more evaluable patients show a “positive” response, the treatment achieves the expected “response” rate of 20%.

The safety-run in will require 6 patients (with a potential for 6-12 more if dose de-escalation is required). The Phase II study will require a total of 24 patients on MTD and thus 18 additionally enrolled patients besides the 6 on MTD during the safety lead-in.

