2 OBJECTIVES AND ENDPOINTS OF THE STUDY

2.1 Objectives

2.1.1 Primary Objectives

1. To assess safety in patients with localized prostate cancer.
2. To characterize B and T cell infiltration within prostate tissue of men with localized prostate cancer treated with neoadjuvant ibrutinib, and to compare B and T cell infiltration to a reference population of untreated patients who underwent RP.

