2.2 Endpoints of the Study

2.2.1 Primary Endpoints

The primary endpoint of the safety-run in part is adverse events (AEs), especially dose limiting toxicity (DLT), as defined in Section 6.1.4.

The primary endpoint of the phase II study include: the change in infiltration of CD20+ B cells, IL-10+ B cells, CD3+ T cells, CD8+ cytotoxic T cells, effector CD4+FOXP3- T cells, and CD4+FOX3+ T regulatory cells in pre-treatment biopsy, RP tissue, and reference RP tissue quantitated by immunohistochemistry (IHC). Patients will be considered to have a positive response if there is ≥ 2 fold decrease from pre-treatment to post-treatment, or considered to have a negative response if there is < 2 fold decrease. The proportion of patients who have “positive” responses will be evaluated.

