12.6.2.2 Intratumoral Immune Infiltration

For all subjects, immune cell subsets and localization will be summarized by changes from baseline to after treatment. Patients will be considered to have a positive response if there is ≥ 2 fold decrease in the number of B cells, or considered to have a negative response if there is < 2 fold decrease in the number of B cells. The proportion of patients who have “positive” responses will be reported, with 95% confidence intervals. Descriptive statistics will be used to describe pre-treatment biopsy immune infiltration, post-treatment RP immune infiltration, and immune infiltration of reference RP tissue.

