12.7 Reference Population

As discussed in the introduction (Section 1.1), in a prior study of neoadjuvant Sipuleucel-T, a negative control was felt to be important to be confident that the observed changes in the study population were due to treatment effect since the effect of systemic Sip-T administration on localized prostate cancer was unknown. Therefore, a group of 12 patients who had undergone RP at UCSF without any neoadjuvant therapy, were selected prior to undergoing any tissue analyses, and were matched to the study population using the UCSF CAPRA-S score for preoperative risk stratification - were used as a negative control. These patients were selected from the surgical population at UCSF who provided separate, written consent to the use of their RP specimens for research purposes.

Similarly, in this study, a cohort of 12 patients not treated with any neoadjuvant therapy will be used as a negative control, since the effect of neoadjuvant ibrutinib in prostate cancer tissue is unknown. Patients will be selected from the RP population at UCSF or Washington University who provided separate, written consent to the use of their RP specimens for research purposes, and will be matched to the phase II study population using the UCSF CAPRA-S score for preoperative risk stratification. This analysis will provide confidence that the changes observed in the prostates of treated patients are due to neoadjuvant treatment effect. These 12 patients will not otherwise be included in the analyses as delineated in 12.6.

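### Section 12.3 attributes the 5% null to untreated reference patients for whom the plan provides RP tissue only, and the RP-to-RP comparison behind Section 12.7 has no planned effect estimate

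*Combined protocol and SAP*

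**What the plan says.** - **Response.** Section 12.3 classifies each patient by a 2-fold fall in B cells between biopsy and RP specimen. Section 9.1.2 measures "the change in the number of immune cell infiltration from the pre-treatment biopsy to post-treatment prostatectomy tissue specimens" as the ratio of RP to biopsy, so each man needs both specimens.
- **Null rate.** Section 12.3 tests a 20% response, "compared to a null response of 5% or less of a reference group of patients who underwent RP without neoadjuvant treatment", with a one-sided exact binomial test on 24 patients. The cut-off is worded unclearly and is read here as 4 or more responders.
- **Reference tissue.** Section 2.2.1 lists infiltration "in pre-treatment biopsy, RP tissue, and reference RP tissue quantitated by immunohistochemistry (IHC"). Section 12.7 draws the 12 reference men from those who consented to research use of their RP specimens. No reference biopsy is mentioned anywhere.
- **Role of the reference group.** The second primary objective (Section 2.1.1) includes the aim "to compare B and T cell infiltration to a reference population of untreated patients who underwent RP". Section 12.7 says: "This analysis will provide confidence that the changes observed in the prostates of treated patients are due to neoadjuvant treatment effect".
- **Analysis of the reference group.** Section 12.6.2.2 says: "Descriptive statistics will be used to describe pre-treatment biopsy immune infiltration, post-treatment RP immune infiltration, and immune infiltration of reference RP tissue". Section 12.7 adds: "These 12 patients will not otherwise be included in the analyses as delineated in 12.6".

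**The concern.** The null is worded as a property of untreated patients, but the plan does not collect from them what that property requires. Biopsy cores and RP sections are different specimens. If B-cell density differs between them, or varies enough that 2-fold falls occur without drug, the responder test counts those falls as response. A reader of Section 12.3 would nevertheless take a positive result as beating an untreated rate.

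Treated RP against reference RP is the one planned tissue comparison within a single specimen type, so it is the natural check on this. It has no planned estimate of difference and no interval, so nothing is laid down by which the attribution statement in Section 12.7 can be judged.

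**Working it through.** **1. The plan's own figure.** Inputs from Section 12.3: N = 24, cut-off 4, p0 = 0.05, p1 = 0.20, stated significance level 0.044, stated power 0.818. The probability of 4 or more responders is 1 − Σ(k=0..3) C(N,k) p^k (1−p)^(N−k).
- N = 24, p = 0.05: 1 − (0.2920 + 0.3688 + 0.2232 + 0.0862) = 0.0298.
- N = 24, p = 0.20: 0.736.

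The stated pair is not reproduced at N = 24. It matches N = 27 with cut-off 4 (0.0437 and 0.8177). That is a separate matter and nothing below depends on it.

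**2. Can the reference group supply the 5%?** Response = RP density ÷ biopsy density ≤ 1/2. For treated men the plan provides numerator and denominator. For reference men it provides the numerator only (Sections 2.2.1, 12.6.2.2, 12.7). The rate cannot be calculated from what is planned.

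**3. How much the unmeasured rate matters.** This is the same formula with the true untreated rate varied. The documents give no such rate, so the values above 5% are assumptions. N = 28 is 24 plus the maximum of 4 replacements, because Section 12.4 keeps delayed-RP patients in the analysis; the cut-off is held at 4.

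| Untreated rate | N = 24 | N = 28 |
|---|---|---|
| 3% | 0.005 | 0.009 |
| 5% | 0.030 | 0.049 |
| 8% | 0.12 | 0.18 |
| 10% | 0.21 | 0.31 |
| 15% | 0.50 | 0.62 |

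**4. What the RP-to-RP comparison could deliver.** Assume normal log2 densities with equal SD in 24 treated and 12 reference men. The median half-width of the 95% Hodges-Lehmann interval, by simulation, is about 0.59, 0.74 and 1.10 log2 units at SD 0.8, 1.0 and 1.5. As a rough check, the t-based half-width is 2.032 × SD × √(1/24 + 1/12) = 0.718 × SD, or 0.57, 0.72 and 1.08. Back-transformed, 2^0.59, 2^0.74 and 2^1.10 are factors of about 1.5, 1.7 and 2.1 either way.

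For a true 2-fold shift, the interval excludes no difference with probability 0.91, 0.75 and 0.42 at the three SDs. For a smaller shift, suppose untreated men have zero median biopsy-to-RP change and 5% show a 2-fold fall. The SD of change is then 1/1.645 = 0.608 log2. Reaching 20% responders takes a shift of 0.608 × (1.645 − 0.842) = 0.488 log2, about 1.4-fold. The corresponding probabilities are 0.36, 0.25 and 0.14. They are illustrative only, since zero median change is the very condition in question.

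**The case against.** **A fixed null is normal.** A one-sample exact test always uses one, and the synopsis makes each subject his own control, with the reference cohort as an addition. This stands: the test is not broken. The fault in Section 12.3 is attributing 5% to a reference group instead of stating it as an assumption.

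**The text is not that definite.** Section 12.3 does not say that its reference group is the 12 men of Section 12.7, and reference biopsies are not excluded. Both points stand. The link is an inference, made because no other untreated group appears. If 5% came from elsewhere, no source is given and the gap is the same. Biopsies are not ruled out, but they are never provided for.

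**Two-sample tests are already listed.** Section 12.6.1 names the t-test and the Wilcoxon rank-sum test, but in the paragraph on demographics and baseline characteristics and without naming the reference cohort. Section 12.6.2.2 governs this endpoint and is descriptive.

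**Description suits 12 non-randomised controls.** This would be a fair choice if Section 12.7 did not rest attribution to treatment on it. Low precision is a reason to show an interval and claim less.

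A reader might infer that the true false-positive risk is 20% to 50%, or that the responder test is invalid. The documents do not support this. They give no untreated rate above 5%, and at 5% the risk stays below 0.05 at both N = 24 and N = 28.

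**Conclusion.** The point holds in limited form and should be corrected. As planned, the reference group cannot supply or check the 5% that Section 12.3 attaches to it, so 5% is an assumption without a stated source. The ≥4 rule has a false-positive risk of 0.030 at N = 24 if that assumption is right. The risk rises steeply if it is not, to 0.12 at 8% and 0.21 at 10%, both assumed rates.

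Separately, a comparison that belongs to a primary objective, and on which Section 12.7 rests attribution to treatment, has no pre-specified effect estimate or interval. The conclusion rests on reading the Section 12.3 reference group as the 12 men of Section 12.7, and on the absence of any provision for their biopsies. It does not show that 5% is wrong.

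**What to change.** 1. **Section 12.3.** Call 5% an assumed value, not a rate of the reference group. Report the false-positive risk of the ≥4 rule over assumed untreated rates of 5% to 15% for the number actually analysed.
2. **Section 12.6.2.2.** Pre-specify the treated-RP minus reference-RP difference in CD20+ density as a Hodges-Lehmann shift on the log2 scale with a 95% confidence interval.
   - *Population:* patients treated at the phase 2 dose level with evaluable RP tissue (24, plus any delayed-RP replacements). Show the three UCSF 2-week patients and any de-escalated cohort separately, so that regimens are not pooled.
   - *Zero counts:* fix the offset before group labels are joined to the densities, for example half the smallest non-zero density observed.
   - *Matching:* show CAPRA-S by group and add a CAPRA-S-adjusted or stratified estimate as a sensitivity analysis.
   - *Other subsets in Section 2.2.1:* estimates with intervals, labelled supportive, without p-values.
   - *Status:* the responder test stays as it is, and this estimate is not a success criterion.
3. **Section 12.7.** State that the 12 men enter this comparison and no other Section 12.6 analysis. Replace the attribution sentence with one limited to what the interval supports. Note that the controls are not randomised and may come from another site ("Patients will be selected from the RP population at UCSF or Washington University", whereas Section 6.1.3 places study RPs at Washington University). Report the site of each specimen.

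**Cost.** Wording, plus one estimate per subset and a sensitivity analysis on tissue already planned. It does not verify the 5%. An interval of about ±0.6 to 1.1 log2 units means that the attribution claim will probably have to be weaker than the one now written.
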